10.2.3. Safety Population

The safety population includes all randomized subjects who received at least 1 dose of IP. The safety population will be used for all safety analysis. Subjects will be analyzed according to the treatment actually received.

10.3. Sample Size and Power Considerations

The equality of OS curves will be compared between the azacitidine and placebo treatment groups using a stratified log-rank test. Assuming a median OS of 16 months in the placebo treated group (), a median OS of 22.9 months in the azacitidine treated group (43% improvement), and a study duration of 60 months with a drop-out rate of 5% from both treatment groups, over the duration of the study, this design requires 330 deaths and approximately 460 subjects (230 per treatment arm) to be randomized in order to achieve at least

90% power to detect a constant hazard ratio of 0.70 and demonstrate a statistically significant difference in OS. It is assumed that the OS distribution is exponential with a constant failure (hazard) rate and that accrual is non-uniform during an accrual period of 36 months with 25% of the subjects accrued during each of the first 2 years of enrollment (50% accrued at 24 months) and the remaining 50% accrued during the last year of enrollment. Sample size calculations are based on a one-sided alpha of 0.025 with one interim analysis for futility after 30% of the events have occurred.

Sample size was calculated using the East[®] Version 5.4 software system ([REDACTED]).

10.4. Background and Demographic Characteristics

Demographic and baseline disease characteristics will be summarized by treatment group for the ITT, mITT, and safety populations. Subjects' age, height, weight, body mass index (BMI), and continuous baseline characteristics will be summarized using descriptive statistics (N, mean, SD, median, minimum, maximum), while age group, gender, race and other categorical variables will be provided using frequency tabulations (count, percent) by treatment group. Summaries of baseline disease characteristics will include CR/CRi status following induction therapy, whether the subject received consolidation therapy following induction therapy, prior history of MDS, time since initial AML diagnosis, ECOG performance status, bone marrow blasts (%), ANC ($10^9/L$), hemoglobin (g/dL), platelet counts ($10^9/L$), and cytogenetic risk classification. For laboratory and vital sign measures, the most recent assessment on or prior to the date of randomization will be used for baseline.

Medical history data (coded by the Medical Dictionary for Regulatory Affairs [MedDRA] dictionary) will be summarized using frequency tabulations by treatment group, system organ class and preferred term for the ITT, mITT, and safety populations.

10.5. Subject Disposition

Subject disposition (analysis population allocation, discontinued, along with primary reason for discontinuation) will be summarized using frequency tabulations for both treatment and follow-up phases. A summary of subjects enrolled by site and by country will be provided. Major protocol violations will be summarized using frequency tabulations for the ITT population. Supportive corresponding subject listings will also be provided.

10.6. Efficacy Analysis

All efficacy analysis will be performed on the ITT population. Key efficacy analysis will be performed on the mITT population as supportive evidence and to assess the robustness of the efficacy findings. Subjects will be analyzed according to randomized treatment group. Refer to Section 3.1 and Section 3.2 for the primary and secondary efficacy endpoints, respectively.

A sequential gate-keeping approach will be used to control the overall type I error rate in order to perform hypothesis testing on multiple endpoints. Two endpoints, the primary efficacy endpoint of OS and the key secondary endpoint of RFS, will be tested sequentially in the given, pre-specified order. The primary efficacy endpoint will be tested first at the two-sided 0.05 significance level. In order to preserve the overall alpha level at 0.05 across the OS and RFS

endpoints, formal statistical inference for the RFS analyses can only be made if superiority of azacitidine is demonstrated for the primary efficacy endpoint, OS, at the two-sided 0.05 significance level.

Other than the pre-specified sequential testing of OS and RFS, no additional alpha adjustments for multiplicity will be made.

10.6.1. Primary Efficacy Analysis

The primary efficacy endpoint of OS is defined as the time from randomization to death from any cause and will be calculated using randomization date and date of death, or date of last follow-up for censored subjects. All subjects will be followed until drop-out, death, or study termination. Drop-out may be due to withdrawal of consent from further data collection or loss to follow-up. Subjects who drop-out or are alive at study termination will have their OS times censored at the time of last contact, as appropriate.

The primary efficacy analysis will be conducted for the ITT population and will compare the OS distributions between the two treatment groups. The null hypothesis for testing the primary efficacy endpoint, time to death from any cause, is that the overall survival distributions for the two treatment groups are equivalent. The OS curves will be estimated using Kaplan-Meier (KM) methods. A stratified log-rank test, stratifying by age at time of induction therapy (55-64 years, ≥ 65 years), prior history of MDS (Yes / No), whether consolidation therapy was administered (Yes / No), and cytogenetic risk category at time of induction therapy (intermediate-risk, poor-risk), at a two-sided alpha level of 0.05, will be used to compare the survival distributions between the two treatment groups. The p-value from the stratified log-rank test will be the confirmatory p-value. Kaplan-Meier estimates for median OS as well as the 25th and 75th percentiles and associated two-sided 95% CIs will be summarized for each treatment group, unadjusted for the stratification variables. In addition, both the numerical difference and the 95% CI of the difference, in the median, 25th, and 75th percentiles between the two treatment groups will be presented for the un-stratified analysis. Plots of the KM survival curves will be presented for the two treatment groups, without adjustment for the stratification variables.

A stratified Cox proportional hazards model will be used to estimate the corresponding hazard ratio and 95% CI for azacitidine relative to placebo. Additionally, KM methods will be used to estimate the 1-year and 2-year survival probabilities for time to death from any cause. Estimates of the 1-year (365 days) and 2-year (730 days) survival probabilities and corresponding 95% confidence intervals will be presented by treatment group.

Median follow-up time, by treatment and overall, will be estimated using KM methods. The analysis of the OS endpoint will be repeated for the mITT-population as a supportive/exploratory analysis.

In order to assess the potentially confounding effects of other cancer therapy received subsequent to the protocol therapy on the survival estimates, an exploratory analysis based on the ITT population, will be performed using modified censoring criteria. For this analysis, subjects who received subsequent therapy for AML following discontinuation from their protocol therapy will be censored on the date that the subsequent therapy was started regardless of their survival status at the time of the final analysis. This exploratory modified time-to-death endpoint will be analyzed using the same methods as described above for the primary efficacy analysis.

10.6.2. Secondary Efficacy Analyses

10.6.2.1. Key Secondary Efficacy Analyses

Relapse-free survival (RFS) is defined as the interval from the date of randomization to the date of documented relapse after CR or CRi or death from any cause, whichever occurs first. Subjects who are still alive without documented relapse after CR or CRi, or who were lost to follow-up without documented relapse, will be censored at the date of their last response assessment. Relapse after CR or CRi is defined according to the IWG AML response criteria ([Appendix E](#)).

The analysis of RFS will be performed using the ITT population and will be analyzed using the same methods as those used for the primary efficacy analysis of OS. The p-value from the stratified log-rank test will be the confirmatory p-value.

The analysis of the RFS endpoint will be repeated for the mITT-population as a supportive/exploratory analysis. Additional sensitivity analyses, based on the ITT population, will be performed using modified RFS definitions. For these analyses of RFS, subjects lost to follow-up without documented relapse or death will be 1) considered as having an event; and 2) considered as having an event if they were randomized to the azacitidine treatment group and censored if they were randomized to the placebo treatment group. The event/censoring time will be the date of the last response assessment.

In order to assess and compare the modified definition of AML relapse being used in this protocol as criteria for discontinuation from treatment (ie, appearance of > 15% blasts in the bone marrow or peripheral blood) with respect to the IWG definition of relapse after CR or CRi ([Appendix E](#)), an exploratory analysis based on the ITT population, will be performed for RFS using this modified definition of relapse. For this analysis of RFS, relapse after CR or CRi is defined as the appearance of > 15% blasts in the bone marrow or peripheral blood. Subjects who are still alive without documented relapse after CR or CRi or who were lost to follow-up without documented relapse will be censored at the date of their last response assessment. This exploratory modified RFS endpoint will be analyzed using the same methods as described above for the key secondary efficacy analysis.

10.6.2.2. Additional Secondary Efficacy Analyses

The time-to-event secondary efficacy variables will be analyzed similarly to the primary efficacy variable without stratification. Kaplan-Meier methods will be used to estimate time-to-event curves, unless otherwise specified. Counts and percentages will be used to describe categorical secondary variables. Secondary efficacy analyses will be performed on the ITT population unless otherwise specified.

Time to relapse from CR/CRi is defined as the interval from the date of randomization to the date of documented relapse after CR or CRi, as defined according to the IWG AML response criteria ([Appendix E](#)). Time to relapse will be analyzed using a competing risk analysis where death without documented relapse is treated as a competing risk for relapse from CR/CRi. Subjects who are lost to follow-up without documented relapse or are alive at last follow-up without documented relapse will be censored at the date of their last response assessment. The cumulative incidence function for time to relapse from CR/CRi will be summarized for each treatment group. Summary statistics will include the cumulative incidence estimate of the

median time to relapse and the one-year cumulative incidence of relapse for each treatment group.

Time to discontinuation from treatment will be assessed as an estimate of treatment failure/tolerability and is defined as the interval from the date of randomization to the date of discontinuation from IP. Subjects who are ongoing in treatment at the time of study closure will be censored at the date of last visit.

Time to discontinuation from treatment will be analyzed using a competing risk model with reason for treatment discontinuation classified as:

- Disease relapse
- Adverse event(s)
- Became eligible for bone marrow or stem cell transplant
- Withdrawal of consent / lost to follow-up / protocol violation
- Death

Cumulative incidence curves will be estimated and summarized for each specific reason for discontinuation from treatment by treatment group.

Additionally, time to discontinuation from treatment will be analyzed using KM methods.

10.7. Safety Analysis

All safety analyses will be performed on the safety population.

Adverse Events will be coded using MedDRA. Adverse event listings will include the verbatim term and the MedDRA preferred term. Treatment-emergent AEs (TEAEs) will be summarized by worst severity grade, system organ class, and preferred term. Treatment-emergent AEs leading to death or to discontinuation from treatment, AEs classified as CTCAE (Version 4.0) Grade 3 or Grade 4, AEs related to IP, and SAEs will be summarized separately. Time to discontinuation from the study due to AE will be summarized using KM methods. Listings of all deaths and all SAEs, regardless of when they occurred, will also be generated. Development of a SPM will be documented as an SAE (considered to be at least an “important medical event” even if no other seriousness criteria apply) throughout a subject’s duration in the study (signing of ICD through the follow-up period of the study).

Clinical laboratory results will be summarized descriptively by treatment group, which will also include a display of change from baseline. Laboratory values outside of the normal ranges will be identified. Clinically significant hematologic and non-hematologic laboratory abnormalities that meet Grade 3 or Grade 4 criteria according to the CTCAE will be listed and summarized. Graphical display of select laboratory parameters over the course of the study will be provided.

Vital sign measurements and ECOG performance status will be listed for each subject at each visit. Descriptive statistics for the vital signs and ECOG performance status, both observed values and changes from baseline, will be summarized by treatment group.

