11. ADVERSE EVENTS

11.1. Monitoring, Recording and Reporting of Adverse Events

An AE is any noxious, unintended, or untoward medical occurrence that may appear or worsen in a subject during the course of a study. It may be a new intercurrent illness, a worsening concomitant illness, an injury, or any concomitant impairment of the subject's health, including laboratory test values (as specified by the criteria below), regardless of etiology. Any worsening (ie, any clinically significant adverse change in the frequency or intensity of a pre-existing condition including AML relapse) should be considered an AE. A diagnosis or syndrome should be recorded on the AE page of the CRF rather than the individual signs or symptoms of the diagnosis or syndrome.

An overdose, accidental or intentional, whether or not it is associated with an AE, or abuse, withdrawal, sensitivity or toxicity to an IP should be reported as an AE. If an overdose is associated with an AE, the overdose and AE should be reported as separate terms.

All subjects will be monitored for AEs during the study. Assessments may include monitoring of any or all of the following parameters: the subject's clinical symptoms, laboratory, pathological, radiological or surgical findings, physical examination findings, or other appropriate tests and procedures.

All AEs will be recorded by the Investigator from the time the subject signs informed consent to 28 days after the last dose of IP or until the last study visit, whichever period is longer. Adverse events and SAEs will be recorded on the AE page of the CRF and in the subject's source documents. All SAEs must be reported to Celgene Drug Safety within 24 hours of the investigator's knowledge of the event by facsimile, or other appropriate method, using the SAE Report Form, or approved equivalent form. Please note that SPMs will be monitored as events of interest throughout the duration of the study including post treatment follow-up period and must be reported as SAEs regardless of the treatment arm the subject is in.

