12. DISCONTINUATIONS

The following events are considered sufficient reasons for discontinuing a subject from the IP / treatment:

- Disease relapse
Subjects will be discontinued from treatment when they meet the following criteria.
 - Appearance of > 15% blasts in the bone marrow or peripheral blood; and
 - The above occurrence should be attributed to relapse following CR/CRi, and not attributable to any other cause (eg, bone marrow regeneration after consolidation therapy or myeloid growth factor administration).
- AE(s)
- Subject withdraws from active treatment but continues follow-up
- Subject becomes eligible (per Investigator) for allogeneic bone marrow or stem cell transplantation during treatment period
- Death
- Lost to follow up
- Protocol violation

Prior to discontinuing IP treatment for a subject assessed to have disease relapse, the Investigator may contact the Medical Monitor and forward appropriate supporting documents for review and discussion.

The reason for discontinuation will be recorded in the CRF and in the source documents.

All subjects discontinued from protocol prescribed treatment for any reason should undergo Treatment Discontinuation procedures including pregnancy test for FCBP. Additionally, all subjects discontinued from protocol prescribed treatment will be followed for a period of 28 days following the last dose of IP or until the date of the last study visit, whichever is later, for the collection of adverse events. Discontinued subjects will not be replaced.

During the follow-up period, all subjects should be followed every month for the first year and then every 3 months thereafter until death for collection of information on survival, AML relapse, monitoring for SPM and subsequent AML therapies, unless the subject has specifically withdrawn consent from further follow-up. Documentation such as laboratory or pathology reports, bone marrow and/or peripheral blood reports supporting the AML relapse will be requested and collected. The Investigator must make every effort to obtain information regarding the subject's survival status before determining the subject is lost to follow-up.

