### **Time to discontinuation from treatment**

Time to discontinuation from treatment will be assessed and is defined as the interval from the date of randomization to the date of discontinuation from IP. Subjects who are ongoing in treatment at the time of study closure will be censored at the date of last visit.

Time to discontinuation from treatment will be analyzed using a competing risk model with reason for treatment discontinuation classified as:

- Disease relapse
- Adverse event(s)
- Became eligible for bone marrow or stem cell transplant
- Withdrawal of consent / lost to follow-up / protocol violation /Other
- Death

Cumulative incidence curves will be estimated and summarized for each specific reason for discontinuation from treatment by treatment arm.

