- serious TEAEs by decreasing order of frequency of PT;
- serious TEAEs related to study medication;
- serious TEAEs with severity of grade 3 or 4;
- serious TEAEs related to study medication with severity of grade 3 or 4;
- TEAEs leading to study medication discontinuation;
- TEAEs leading to dose reduction of study medication;
- TEAEs leading to dose interruption of study medication;
- TEAEs leading to dose interruption and reduction of study medication;
- TEAEs by sex;
- TEAEs by age group (< 65, ≥ 65 to 75, and ≥ 75years);
- TEAEs by race group (White, Asian, Black or Others);
- TEAEs by ECOG performance status (0 or 1, 2 or 3)

Additionally, the incidence rate per 100 person-years will be summarized for all TEAEs and Grade 3 or 4 TEAEs by system organ class, preferred term, and treatment arm. The incidence rate per 100 person-years is calculated as  $(100*n)/T$ , where n is the number of subjects with the given AE at the system organ class or preferred term level, and T is total person-years of exposure. If a subject has multiple events with the same preferred term, then the time to the first event is used. For subject with no event, time to earlier of last dose + 28 days or death date is used.

Subjects with multiple events reported for the same preferred term will be counted only once per system organ class and preferred term level. For summaries by severity (CTCAE grade), subjects with multiple events at the preferred term level will be counted once and for the highest reported severity. For summaries by treatment cycle, subjects with multiple events reported with

a start date within the same cycle for the same preferred term will be counted once per system organ class level and preferred term level within the cycle.

In summaries of TEAEs related to study medication, if a subject reports multiple occurrences of the same AE, only the related occurrence will be summarized. Adverse events with missing relationship to study medication will be imputed as related to study medication.

Additional safety analysis may be performed, displayed and summarized, when deemed necessary.

To assess the safety profile among subjects who have dose escalation, defined as subjects who have at least one assigned dose of 300mg × 21/28 days, the following summary tables will be provided in subjects with dose escalation:

- First occurrence of TEAE by dose schedule period (300mg × 14/28days, 300mg × 21/28days);

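### Protocol 10.7 plans a Kaplan-Meier summary of discontinuation due to AE, which under the usual censoring overstates that probability; the SAP neither carries this summary nor withdraws it (minor)

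*Protocol*

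**What the plan says.** Protocol 10.7 (safety population): "Time to discontinuation from the study due to AE will be summarized using KM methods". No censoring rule follows, and no comparison between arms is planned for this item.

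Protocol 10.6.2.2 (ITT unless otherwise specified) handles a closely related event differently: "Time to discontinuation from treatment will be analyzed using a competing risk model with reason for treatment discontinuation classified as" relapse, adverse event, transplant eligibility, a combined category of consent withdrawal, loss to follow-up and protocol violation, and death. The output is specific to each cause: "Cumulative incidence curves will be estimated and summarized for each specific reason for discontinuation from treatment by treatment group". The same section adds: "Additionally, time to discontinuation from treatment will be analyzed using KM methods". As worded, that last analysis covers discontinuation for any reason.

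SAP 11.3.2, under time to discontinuation from treatment, repeats the competing-risk analysis: "Cumulative incidence curves will be estimated and summarized for each specific reason for discontinuation from treatment by treatment arm". SAP 11.3 places the secondary efficacy endpoints in the ITT population.

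On AE discontinuation, the visible SAP section 12 has frequency tables (for example "TEAEs leading to study medication discontinuation" in 12.1) and listings, and no Kaplan-Meier curve. SAP section 15, which lists changes to the protocol's statistical section, names two dropped RFS sensitivity analyses and nothing about 10.7.

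The event itself is described in two ways. Protocol 10.7 speaks of leaving the study, and SAP section 6 lists adverse event among the CRF reasons for leaving the study. Protocol 10.6.2.2, Protocol 12 and SAP 11.3.2 speak of leaving treatment, and Protocol 12 keeps those subjects in follow-up.

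**The concern.** A Kaplan-Meier curve for one cause of stopping ordinarily censors every other exit. Censoring treats the subject as still able to have the event later. A subject who has died cannot later stop for an AE, and a subject already off treatment for another reason cannot stop treatment for one. These are competing events, and with them 1-KM no longer estimates the proportion who stop for an AE: it is too high whenever both hazards are positive.

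At stake is a tolerability figure. A reader would take 1-KM as the chance of having to stop for an AE. The excess depends on each arm's rate of competing exits, so it need not be the same in both arms.

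**Working it through.** **Inputs from the documents.** Protocol 10.3 and SAP 4.4: median OS 16 months (placebo) and 22.9 months (azacitidine), exponential survival, 330 deaths, about 460 subjects (230 per arm), hazard ratio 0.70, one-sided alpha 0.025, at least 90% power. Neither document gives a rate of AE discontinuation, relapse or death on treatment.

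**The plan's own figure.** There is none for AE discontinuation. The design from which the OS medians are taken is internally consistent: 16/22.9 = 0.699, 22.9/16 - 1 = 43%, and Schoenfeld's formula gives 331 deaths against 330 stated (power 90.0% with 330).

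**Formulas.** Constant cause-specific hazards, *a* for stopping due to AE and *c* for competing exits:

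- 1-KM at time t = 1 - exp(-a·t)
- Cumulative incidence at time t = a/(a + c) × [1 - exp(-(a + c)·t)]

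**Death as the only competing exit, at the plan's OS rates.** Placebo: c = ln 2/16 = 0.0433 per month. Azacitidine: c = ln 2/22.9 = 0.0303 per month. The values of *a* are assumed.

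For a = 0.01 and t = 24:

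- 1-KM = 1 - exp(-0.24) = 21.3% in both arms.
- Placebo: 0.01/0.0533 × [1 - exp(-1.280)] = 0.1876 × 0.722 = 13.5%.
- Azacitidine: 0.01/0.0403 × [1 - exp(-0.966)] = 0.2483 × 0.620 = 15.4%.

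| Assumed a (per month) | Month | 1-KM | Cumulative incidence, placebo | Cumulative incidence, azacitidine |
|---|---|---|---|---|
| 0.0025 | 12 | 3.0% | 2.3% | 2.5% |
| 0.005 | 24 | 11.3% | 7.1% | 8.1% |
| 0.01 | 12 | 11.3% | 8.9% | 9.5% |
| 0.01 | 24 | 21.3% | 13.5% | 15.4% |

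With the same AE hazard in both arms, 1-KM is identical, while the cumulative incidences at 24 months for a = 0.01 differ by 15.4 - 13.5 = 1.9 points.

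**Wider range.** Here the true cumulative incidence is fixed and the median time to a competing exit runs from 6 to 22.9 months. Medians of 6 to 12 months are assumed, to stand for relapse or death; 16 and 22.9 are the OS medians.

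| True cumulative incidence | Excess of 1-KM when it is the 12-month value (points) | Excess of 1-KM when it is the 24-month value (points) |
|---|---|---|
| 2% | 0.4 to 1.7 | 0.8 to 3.8 |
| 5% | 1.0 to 4.1 | 2.0 to 9.3 |
| 10% | 1.9 to 8.1 | 3.9 to 17.7 |
| 15% | 2.8 to 11.8 | 5.8 to 25.1 |

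The direction is fixed. The size runs from under half a point to more than 20 points, depending on rates that the documents do not give.

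**The case against.** The strongest reply is that the right analysis is already planned. Protocol 10.6.2.2 and SAP 11.3.2 both give a cumulative incidence curve for AE as a reason for stopping treatment, and the visible SAP outputs contain no Kaplan-Meier curve for AE discontinuation. A reader might infer from Protocol 10.7 that the trial will report a toxicity-stopping probability several points too high. The documents do not support that: the biased figure is not among the visible SAP outputs, and the number of points rests on assumed hazards. Some SAP sections are missing from the public text, so this absence can be judged only on what is visible.

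A reader might also infer that relapse always rules out a later AE discontinuation. It does not. Under Protocol 8.2.6, subjects with blasts above 5% but no greater than 15% may continue treatment. Those who stop treatment for relapse stay in follow-up (Protocol 6.14 and 12), so they could still leave the study later. Protocol 11.1 counts as an AE "any clinically significant adverse change in the frequency or intensity of a pre-existing condition including AML relapse". Death is a competing event on either reading; relapse is one only where it ends treatment and the event is stopping treatment.

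Nor can the reference in 10.7 to leaving the study be called a slip, because SAP section 6 lists adverse event as a reason for leaving the study. As written, the 10.7 summary and the 10.6.2.2 analysis differ in population and in event, so their figures could differ whatever the estimator.

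Finally, the censoring is inferred from the method and not written down, and the item is descriptive. All these replies limit the point. What they leave is a protocol analysis with a known upward bias that the SAP does not visibly carry out and does not withdraw.

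**Conclusion.** The point stands as a minor one. Under the usual censoring convention, the summary in Protocol 10.7 overstates the probability of stopping for an AE. In the example with a = 0.01 per month, the excess at 24 months is 7.8 points for placebo and 6.0 for azacitidine (unrounded differences). At a = 0.0025 per month it is 0.6 and 0.5 points at 12 months.

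These figures rest on constant hazards, an assumed AE-stopping rate, and the OS medians as the only competing hazard. If the event is stopping treatment, the OS rate is only a stand-in: death on treatment may be rarer than death overall, and relapse that ends treatment adds to the competing exits.

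The status of the summary is also unclear, since a programmer cannot tell from the visible text whether it is still due. Alpha, power, OS and RFS are unaffected.

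**What to change.** Do one of two things:

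- In Protocol 10.7, replace the Kaplan-Meier summary with the cumulative incidence of discontinuation due to AE in the safety population, with death and the other exits that end treatment as competing events.
- Or record in SAP section 15 that the Kaplan-Meier summary is dropped in favour of the analysis by reason in SAP 11.3.2.

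In either case, reconcile discontinuation from the study (Protocol 10.7, SAP section 6) with discontinuation from treatment (Protocol 10.6.2.2 and 12, SAP 11.3.2). State which event is analysed, because this decides which exits compete with it. The all-cause Kaplan-Meier analysis in Protocol 10.6.2.2 need not change on this account.

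The cost is small. The first option needs a wording change and one more run, on the safety population, of a method that SAP 11.3.2 already plans for ITT. The second needs one line in the SAP.
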